8 EFFICACY ANALYSES

Efficacy analyses will be performed using FAS subjects from the Confirmatory Cohorts only. Only the Overall Confirmatory Cohort will be used for efficacy interpretations. Efficacy parameters will be summarized descriptively (with 95% CIs) by individual Confirmatory Cohorts and for all combined Confirmatory Cohorts. In addition, all efficacy variables will be analyzed by the latest primary cause of seizure (see categories in [Section 4.8](#)) and concomitant use of hypothermia and reported for each subject using data listings.

Seizure efficacy data may also be transformed if needed. The transformation of seizure data to be used (if needed) will be $\log(x + 1)$ where x is the neonate seizure count or the seizure burden.

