- BRV Extension Period (28 days [up to 90 days] of PNA): Subjects can proceed to the BRV Extension Period if they benefit from BRV treatment during the Evaluation Period, in accordance with the Investigator's opinion. All subjects who participate in the BRV Extension Period must be offered entry into the long-term study, if they meet the eligibility criteria. Subjects will participate in the BRV Extension Period until they reach a stable condition that will allow them to enter the long-term study, if epilepsy is confirmed.

The anticipated duration of the BRV Extension Period per subject is up to 28 (+7) days of PNA. Subjects who are not able to be dosed with BRV oral solution at a PNA of 28 days may continue in the BRV Extension Period for an additional 7 days; subjects who are not able to be switched to BRV oral solution by the end of the additional 7 days of the BRV Extension Period will not be eligible for enrollment in the long-term study.

In the event that a long-term study is temporarily not available, subjects are allowed to remain in the BRV Extension Period until they reach a PNA of up to 90 days. For those subjects, the assessments planned for Unscheduled Visits (see [Section 8.1.3.3](#)) will be conducted in intervals of approximately 30 days during the prolonged Extension Period. The treatment with BRV will be managed through IVRS. Before subjects can roll-over to the long-term study, they must have switched to BRV oral solution.

- Subjects must switch to BRV oral solution before entering the long-term study. The timepoint of the switch from iv to oral solution will be at the discretion of the Investigator.

During the BRV Extension Period, subjects may continue receiving the same BRV dose administered at the end of the Evaluation Period; the BRV dose should not be increased, but may be decreased at the discretion of the Investigator.

Down-Titration Period (up to 1 week): A Down-Titration Period of up to 1 week is recommended for subjects in the Confirmatory Cohorts who discontinue BRV treatment prior to completion of the Evaluation Period, who do not proceed to the BRV Extension Period, or start the BRV Extension Period but do not enter the long-term study. The Down-Titration steps and duration may be adjusted at the Investigator's discretion.

- Safety Follow-Up Period: Subjects will proceed to the Safety Follow-Up Period once they complete the Down-Titration Period. The visit will occur 30±3 days after the final administration of BRV.

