8.2.4 Down-Titration Period

A Down-Titration Period of up to 1 week is recommended for subjects who complete the Evaluation Period, but do not enter the BRV Extension Period, discontinue BRV during the Evaluation Period, or start the BRV Extension Period but do not continue into the long-term study for any reason. The Down-Titration steps and duration may be adjusted at the Investigator's discretion.

The following assessments will be performed:

- Vital signs (blood pressure, heart rate, respiratory rate [including apneas], oxygen saturation [pulse oximetry], and body temperature)
- Physical and neurological examination (Sarnat scale for subjects with HIE; physical examination will include a check for the presence of skin rash and skin hypersensitivity; to be performed on the first day of the Down-Titration Period only)
- Primary cause of seizure (HIE, hemorrhage, or infarction; CNS malformations; CNS infections; undetermined causes; to be performed on the first day of the Down-Titration Period only)

- N-PASS
- BRV administration
- At least a 1-hour video-EEG on the final day of the Down-Titration Period (during the Down-Titration Period, additional VEEGs can be performed at the Investigator's discretion)
- AEs as reported by the Investigator
- AEDs, concomitant medications, and medical procedures
- Infusion site reaction monitoring

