8.2.5 Safety Follow-Up Period

Subjects will proceed to the Safety Follow-Up Period once they complete the Down-Titration Period. This visit will occur 30 ± 3 days after the final administration of BRV. The following assessments will be performed:

- Vital signs (blood pressure, heart rate, respiratory rate [including apneas], oxygen saturation [pulse oximetry], and body temperature)
- Physical and neurological examination (Sarnat scale for subjects with HIE; physical examination will include a check for the presence of skin rash and skin hypersensitivity)
- Body weight and length and head circumference
- Confirmation of the primary cause of seizure (HIE, hemorrhage, or infarction; CNS malformations; CNS infections; undetermined causes)
- N-PASS
- Safety laboratory assessments (hematology, biochemistry, liver enzymes, and endocrinology)
- AEs as reported by the Investigator
- AEDs, concomitant medications, and medical procedures
- Medical History (for subjects not entering the long-term study)

For subjects unable to return to the hospital due to COVID-19, the Safety Follow-Up Visit can be performed remotely. In this case vital signs, the physical and neurological examination, biometric and psychometric parameters, and the laboratory assessment may not be performed.

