13.5 Planned efficacy analyses

All efficacy parameters will be summarized descriptively.

Video-EEGs will be assessed locally by the Investigator for any medical decisions or medical interventions. Video-EEGs may also be assessed by a blinded, central reader to support Investigators if needed. The final analysis of VEEG outputs will be based solely on the assessment of a central reader. Efficacy parameters will be summarized descriptively (overall [with CIs]) by cohort. All efficacy variables will be analyzed by the primary cause of seizure (HIE, hemorrhage, or infarction; CNS malformations; CNS infections; undetermined causes) and concomitant use of hypothermia, and reported for each subject using data listings.

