6.7 Primary cause of seizure

Primary cause of seizure will be summarized by cohorts for SS. The summary analysis of the primary cause of seizure should be based on the latest data collected per subject prior to study completion/termination. Listing of all primary causes of seizure will be provided for the SS.

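### Efficacy subgroups use the latest recorded cause of seizure, but after 96 hours the cause is scheduled to be updated only for babies who do not roll over, which can enrich 'undetermined' with babies who benefited

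*SAP*

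**What the plan says.** SAP section 8 sets the rule for every efficacy variable: "In addition, all efficacy variables will be analyzed by the latest primary cause of seizure". Section 8.2.2 repeats it for the main secondary variable, the 3-hour responder proportion. Section 6.7 explains what latest means: the summary is "should be based on the latest data collected per subject prior to study completion/termination".

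The protocol is less specific. Section 13.5 says "All efficacy variables will be analyzed by the primary cause of seizure", with no time point. SAP 4.8 gives none either. SAP Table 3.1 (section 3.10), which lists departures from the protocol's analyses, declares the change from four cause categories to nine but not the timing rule.

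On collection, protocol 8.2.1.1 and 8.2.2 schedule the cause at Baseline and at 96 hours. Protocol 8.2.4 schedules it again at Down-Titration ("undetermined causes; to be performed on the first day of the Down-Titration Period only"), and 8.2.5 schedules it at Safety Follow-Up ("Confirmation of the primary cause of seizure"), 30±3 days after the last dose. On who takes which route, protocol 5.1.2 says: "Subjects can proceed to the BRV Extension Period if they benefit from BRV treatment during the Evaluation Period". This is judged by the Investigator. The same section bars babies switched to another AED from both the Extension Period and the long-term study.

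**The concern.** A subgroup label should be recorded in the same way for every baby, whatever happens after treatment starts. Here, whether the label can still change after 96 hours depends on the route by which the baby leaves the study, and that route depends partly on how the baby did on BRV.

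A cause established late (a genetic or metabolic diagnosis, say) can reach the analysis through the scheduled records only for a baby who does not roll over. A baby who rolls over keeps the 96-hour label. If causes are resolved after 96 hours at all, those leaving 'undetermined' will be mostly babies who stopped BRV. The babies left in 'undetermined' will then look better, and the categories receiving the late diagnoses will look worse, even if BRV works equally well for every cause. A reader of the subgroup tables could take this for a difference by etiology.

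**Working it through.** The plan states no figure on this point, so there is none to reproduce. The check has two parts.

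**1. Scheduled cause records by exit route (Confirmatory Cohorts)**

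| Record | Rolls over | Does not roll over |
|---|---|---|
| Baseline (protocol 8.2.1.1) | yes | yes |
| 96 h (8.2.2) | yes | yes |
| EPV1, EPV2, Unscheduled Visit, Telephone Contact (8.2.3.1 to 8.2.3.4) | not scheduled | not scheduled |
| Down-Titration day 1 (8.2.4) | not reached | yes, if down-titrated |
| Safety Follow-Up (8.2.5) | not reached | yes |

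Table 5-3 agrees. EPV2 collects the epilepsy diagnosis and updated medical history, but not the cause item. Protocol 5.1.3 sends to Safety Follow-Up all babies who do not continue into the long-term study. SAP 3.2.4 counts a rollover baby as complete at EPV2, so that baby's latest scheduled cause is the 96-hour one.

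**2. Size, with no true difference by cause**

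The documents give none of these inputs, so all are assumed:
- b, the share of babies who benefit, equal in every cause: 0.3 to 0.7.
- g, the share of benefiters who roll over: 0.2 to 0.8. Non-benefiters are taken not to roll over, and rollover is taken as unrelated to cause.
- r, the share of babies 'undetermined' at 96 hours whose cause is resolved if it is recorded again later: 0.1 to 0.5.

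Benefit rate among those still 'undetermined' = b(1 − r(1 − g)) / [b(1 − r(1 − g)) + (1 − b)(1 − r)].

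Benefit rate among those moved out = b(1 − g) / [b(1 − g) + (1 − b)], since r cancels.

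Example with b = 0.5, r = 0.5, g = 0.8:
- Still 'undetermined': 0.5 × 0.9 = 0.45 benefiters and 0.5 × 0.5 = 0.25 non-benefiters, so 0.45/0.70 = 0.643.
- Moved out: 0.1/(0.1 + 0.5) = 0.167.

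| True b | Still 'undetermined' | Moved out |
|---|---|---|
| 0.30 | 0.305 to 0.435 | 0.079 to 0.255 |
| 0.50 | 0.505 to 0.643 | 0.167 to 0.444 |
| 0.70 | 0.705 to 0.808 | 0.318 to 0.651 |

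The smallest enrichment of 'undetermined' is 0.305 − 0.300, about 0.5 percentage points. The largest is 0.643 − 0.500, about 14 points.

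In babies: 36 over nine categories is a mean of 36/9 = 4 per category. The share moved out of 'undetermined' is r(1 − bg), from 0.1 × (1 − 0.56) = 0.044 to 0.5 × (1 − 0.06) = 0.47. For a group of four that is 0.2 to 1.9 babies, so at most about two if the categories are evenly filled.

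With the label fixed at 96 hours, the benefit rate in 'undetermined' equals b in every scenario, and the artefact in this model is zero.

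**The case against.** A reader might infer that benefit alone decides who stays in 'undetermined'. The documents do not support that. Benefit opens the Extension Period, but keeping the 96-hour label takes rollover, which also needs a stable condition, confirmed epilepsy, oral BRV and eligibility (protocol 5.1.2, 8.2.3). A baby who benefits but does not roll over proceeds to Safety Follow-Up and has the later record scheduled there.

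A reader might also infer a gross distortion of the 3-hour responder table. Suppose true response is 40%, every responder counts as a benefiter, 70-100% of responders roll over, no non-responder does, and 25-50% of reassessed cases are resolved. Response then appears as 45-57% in 'undetermined' and 0-17% in those moved out. Three things undercut this:
- Protocol 2.3 says most neonatal seizures do not fit the usual meaning of epilepsy, so with epilepsy confirmation as a gate, low rollover is at least as plausible. At 20% rollover and 25% resolution the same formula gives 41.6% (0.32/0.77) and 34.8% (0.32/0.92).
- The 3-hour endpoint rests on the central VEEG reading over hours 1 to 3, whereas Extension entry is the Investigator's opinion at the end of the Evaluation Period. A 3-hour non-responder who is not switched can still enter the Extension, and a 3-hour responder can later be switched.
- Epilepsy confirmation is probably related to cause, which the formula ignores.

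It can fairly be added that cause is a pre-existing attribute, so the latest record is the best-informed diagnosis. The nine categories include genetic epilepsy and inborn errors of metabolism, which may be recognised late. The analyses are descriptive (SAP 4.5), and SAP 6.7 already promises a listing of all recorded causes.

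These arguments limit the size of the problem and weigh against discarding the late diagnosis. They do not make the labels comparable across exit routes, and a listing does not correct the planned subgroup tables.

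**Conclusion.** The point holds as a matter of unequal ascertainment. SAP 6.7, 8 and 8.2.2 use the latest cause, and a cause record after 96 hours is scheduled only for babies who do not roll over. Late moves out of 'undetermined' can therefore occur mainly among babies who leave BRV, which can tilt that group towards benefiters.

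The 0.5 to 14 point range depends entirely on the assumed benefit, rollover and resolution rates. It also presumes that causes do change after 96 hours; the repeat records suggest this can happen, but not how often. The range describes Investigator-judged benefit. For the 3-hour responder rate the effect is diluted by an amount that cannot be worked out from the documents. Only the descriptive subgroup tables are touched. This is a cheap improvement, not a threat to the trial's main efficacy result.

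**What to change.** In SAP 6.7, 8 and 8.2.2, define the main efficacy subgroup by the 96-hour cause record, using the Baseline record if the 96-hour one is missing, and state how many babies needed that fallback. Babies who stop BRV early are still meant to complete the 96-hour assessments apart from BRV PK sampling (protocol 5.1.2), so the record is scheduled for every baby who stays in follow-up. Keep the latest-cause subgroup table as a sensitivity display, with a shift table from the 96-hour to the latest cause. Add the timing rule to SAP Table 3.1.

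The cost is SAP wording, one derivation and one extra display; no new data are needed. The small downside is that causes established after 96 hours appear only in the sensitivity display. The 96-hour record is itself made after the 3-hour outcome, but it is scheduled at the same time on every route, which is what the comparison needs.

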8.1 Endpoint definitions and derivations

8.1.1 BRV responder and non-responder definitions

A BRV responder is defined as a subject who achieves the following reduction in seizure burden (ENS in minutes per hour) without need for rescue medication, compared to the seizure burden measured during the Baseline Period immediately prior to BRV administration, evaluated for a 2-hour period starting 1 hour after the start of initial BRV treatment:

- At least 80% reduction (≥ 80 percent change) in non-severe seizure burden
(Non-severe seizure burden is defined as $\leq 50\%$ seizure activity on video-electroencephalography (VEEG) in all 30-minute timespans)

OR

- At least 50% reduction (≥ 50 percent change) in severe seizure burden

(Severe seizure burden is defined as >50% seizure activity on VEEG in any 30-minute timespan. Timespans of 30 minutes refer to the following intervals within the 2-hour period: 0 to \leq 30 minutes, >30 to \leq 60 minutes, >60 to \leq 90 minutes, and >90 to \leq 120 minutes.)

Subjects not meeting the BRV responder definition are classified as BRV non-responders. In addition, subjects who drop out due to lack of BRV efficacy, are switched over to another AED treatment, or are administered any rescue medication (any treatment initiation with a new AED, or any increase of dose or frequency of an existing concomitant AED for the treatment of seizures during the Evaluation Period - including BZDs) during the first 3 hours after initiation of BRV treatment will be considered BRV non-responders.

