4.2.1 Secondary efficacy variables

The main secondary efficacy variable is as follows:

- Proportion of responders to BRV treatment from Baseline to 3 hours after the initial BRV dose

A BRV responder is defined as a subject who achieves the following reduction in seizure burden (ENS in minutes per hour) without need for rescue medication, compared to the seizure burden measured during the Baseline Period immediately prior to BRV administration, evaluated for a 2-hour period starting 1 hour after the start of initial BRV treatment:

- At least 80% reduction in nonsevere seizure burden

(Nonsevere seizure burden is defined as $\leq 50\%$ seizure activity on VEEG in all 30-minute timespans)

OR

- At least 50% reduction in severe seizure burden

(Severe seizure burden is defined as $> 50\%$ seizure activity on VEEG in any 30-minute timespan). Timespans of 30 minutes refer to the following intervals within the 2-hour period: 0 to ≤ 30 minutes, > 30 to ≤ 60 minutes, > 60 to ≤ 90 minutes, and > 90 to ≤ 120 minutes.

For this study, an ENS is defined as an EEG seizure lasting for at least 10 seconds on VEEG. Baseline seizure burden is defined as seizure burden measured on the continuous VEEG (total ENS in minutes per hour) during a period of up to 1 hour immediately prior to the first administration of study drug.

In addition, the secondary efficacy variables will include:

- Proportion of subjects with at least 80% reduction in nonsevere seizure burden from Baseline to 3 hours after the initial BRV treatment
- Proportion of subjects with at least 50% reduction in severe seizure burden from Baseline to 3 hours after the initial BRV treatment
- Absolute reduction in average seizure burden measured by continuous VEEG from Baseline to the end of the 96-hour Evaluation Period
- Percent reduction in average seizure burden measured by continuous VEEG from Baseline to the end of the 96-hour Evaluation Period
- Proportion of BRV responders at the end of the 96-hour Evaluation Period
- Proportion of subjects who are seizure-free (100% reduction in seizure burden from Baseline) at 24 hours following the start of initial BRV treatment, categorized by subjects with nonsevere or severe seizure burden at Baseline

- Time to reduction in seizure burden for BRV responders (defined as the first timepoint when BRV responder criteria are met)
- Seizure freedom at the end of the Down-Titration Period

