8.1.2 Baseline seizure burden

Baseline seizure burden is defined as seizure burden measured on the continuous VEEG (total ENS in minutes per hour) during a period of up to 1 hour immediately prior to the first administration of study medication.

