8.1.2.1 Baseline non-severe seizure burden

Baseline non-severe seizure burden is defined as seizure activity (total ENS duration in minutes) for \leq 15 minutes in all of the following 30-minute time periods: 0-30 and >30-60 minutes during the 1-hour Baseline Period. For example, if total ENS duration of 18 minutes occurred as 9 minutes of ENS duration in each of any two 30-minute time periods or 18 minutes of ENS are distributed over several 30 minute time intervals so that the ENS duration in each interval is \leq 15 minutes, then the baseline seizure burden is non-severe.

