8.1.5 Percent change in baseline seizure burden

Percent change in baseline seizure burden is defined as a difference between average per hour seizure burden at baseline (calculated over the 1-hour baseline period) and average per hour

seizure burden calculated over given period of time after the start of initial BRV treatment divided by the average per hour seizure burden at baseline and multiplied by 100.

If the percent change is $\geq 80\%$ (reduction in baseline) and baseline seizure burden is non-severe or if the percent change $\geq 50\%$ (reduction in baseline) and baseline seizure burden is severe then this subject is defined as **BRV responder**. No rounding will be applied, one decimal will be considered for comparison (for example, if the percent change is 79.999%, then consider 1 decimal as 79.9% which is less than 80%).

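### SAP 8.1.1 and the protocol's responder definition tie the severe/non-severe split to 30-minute spans of a 2-hour period that Baseline no longer has, which conflicts with the Baseline severity rule in SAP 8.1.2 and 8.1.5

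*SAP*

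**What the plan says.** The main secondary efficacy variable is the proportion of responders. SAP 8.1.1 gives two routes: "At least 80% reduction (≥ 80 percent change) in non-severe seizure burden", or "At least 50% reduction (≥ 50 percent change) in severe seizure burden". Response is "evaluated for a 2-hour period starting 1 hour after the start of initial BRV treatment" (protocol 4.2.1; SAP 8.1.1 agrees).

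Burden is severe if seizures fill more than half of any 30-minute span, and non-severe otherwise. The spans are then specified: "Timespans of 30 minutes refer to the following intervals within the 2-hour period", followed by four half-hours running to 120 minutes. Protocol Sections 1, 4.2.1, 10.1 and 13.5.1 carry the same sentence.

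Three other parts of the SAP treat severity as a Baseline attribute:

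- **8.1.2** measures Baseline burden "during a period of up to 1 hour immediately prior to the first administration of study medication". **8.1.2.1** calls it non-severe if there are at most 15 seizure minutes "in all of the following 30-minute time periods: 0-30 and >30-60 minutes during the 1-hour Baseline Period". **8.1.2.2** calls it severe if either span exceeds 15 minutes.
- **8.1.5** states a responder rule in terms: 80% if Baseline burden is non-severe, 50% if Baseline burden is severe.
- **8.2.4** uses the 8.1.2 classes for the two component endpoints.

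SAP 8.2.1 takes the numerator from Section 8.1 as a whole, which contains both 8.1.1 and 8.1.5. SAP Table 3.1 lists no change to this endpoint from the protocol.

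**The concern.** A Baseline of at most 1 hour (up to 30 minutes in status epilepticus) cannot contain spans that run to 120 minutes. The only 2-hour period in the responder definition is the post-dose response window. A programmer who follows 8.1.1, the section titled as the responder definition and the one that matches the protocol, would classify severity on post-dose EEG. The target would then depend on the outcome: an infant who improves from severe moves to the 80% target, and an infant with one bad post-dose half-hour moves to the 50% target.

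A programmer who follows 8.1.5 would classify on Baseline. Both would be following the SAP, and they could report different responder rates. That rate carries the main efficacy reading: protocol 13.5.1 compares its 95% confidence interval with historical rates to call brivaracetam efficacious, not efficacious or inconclusive. In an open-label single-arm study, the choice between the rules should not be left until data have been seen.

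**Working it through.** The documents give no sample size calculation or power, so there is no design figure to reproduce. The check applies both rules to the same infants.

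**Inputs.** Targets of 80% and 50% (SAP 8.1.1). Severe means more than 15 seizure minutes in a 30-minute span (SAP 8.1.2.2; half of 30 minutes in 8.1.1). Response window of 2 hours. Percent reduction = (Baseline min/h − post-dose min/h) / Baseline min/h × 100 (SAP 8.1.5). The SAP's own examples come out as it states: 9+9 minutes is non-severe, 16+2 is severe.

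**Infants classified differently.**

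| Baseline spans (min) | Post-dose spans (min) | Reduction | 8.1.5 (Baseline class) | Literal 8.1.1 (post-dose class) |
|---|---|---|---|---|
| 20, 20 (severe) | 7, 7, 7, 7 | (40−14)/40 = 65% | target 50%: responder | target 80%: non-responder |
| 10, 10 (non-severe) | 16, 0, 0, 0 | (20−8)/20 = 60% | target 80%: non-responder | target 50%: responder |
| 18 in one 30-min span (severe) | 5, 5, 5, 5 | (36−10)/36 = 72.2% | target 50%: responder | target 80%: non-responder |

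**The literal rule also separates infants with equal reductions.** With Baseline 14+14, post-dose 16, 2, 1, 1 and 5, 5, 5, 5 both average 10 min/h, a reduction of (28−10)/28 = 64.3%. Literal 8.1.1 passes the first, which has the worse half-hour, and fails the second. Under 8.1.5 both fail.

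**Where disagreement can occur.** Only for reductions of at least 50% and below 80%.

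- *Severe at Baseline:* the responder is lost unless some post-dose half-hour still exceeds 15 minutes. Baseline cannot exceed 60 min/h, so a reduction of 50% or more leaves at most 30 min/h, an average of 15 minutes per half-hour. Passing at 50% under the literal rule therefore needs unevenly spread seizures.
- *Non-severe at Baseline:* the responder is gained only if one post-dose span exceeds 15 minutes, which means more than 15/2 = 7.5 min/h. A 50% reduction then requires a Baseline above 15 min/h, and non-severe caps it at 30 min/h. An 80% reduction from 30 min/h would need at most 6 min/h, so every infant who enters this way fails 8.1.5.

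**Size, on assumed inputs only.** The documents give no distribution of burden, seizure length or effect.

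- *Set 1:* 20–60% severe at Baseline; reductions uniform from 0, 30 or 50% up to 100%; seizure minutes split at random over the four spans. Responder rates were 26–76% under 8.1.5 and 23–53% under literal 8.1.1. The smallest fall was 26.4 − 22.8 = 3.6 points and the largest 76.0 − 53.2 = 22.8. Infants gained by the literal rule were 0.1–0.5% of all infants.
- *Set 2:* alternating random seizures and gaps, with varied inputs. The net fall ran from about 0.6 to 14.5 points. With the other inputs held fixed, it shrank as mean seizure length rose from 2 to 15 minutes. Infants gained were 0.0–0.4%.

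**Scale at the planned size.** If all 36 Confirmatory subjects are in the Full Analysis Set, one infant is 1/36 = 2.8 points. Three reclassified infants, for example 19/36 to 16/36, move the exact (Clopper-Pearson) lower 95% limit from 35% to 28%. The SAP does not name an interval method, so the exact interval is an assumption.

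**The case against.** The strongest reply is that the SAP already states the intended rule. Section 8.1.5 says outright that Baseline severity selects the target, 8.1.2.1 and 8.1.2.2 supply the Baseline spans, 8.2.4 uses them, and the 8.2.1 reference to Section 8.1 covers 8.1.5. An analyst who programs 8.1.5 never lets the outcome set the target. The span sentence looks like a leftover: the amendment log shows that Baseline was once 2 hours. That history is not an error in itself. All of this stands as evidence of intent. It does not say which of two conflicting rules governs.

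Three stronger readings are tempting, and the documents do not support them.

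- *That the plan settles on letting the outcome choose the target.* It does not; 8.1.5 says the opposite. The defect is an unresolved conflict.
- *That the protocol supports only a post-dose rule.* Protocol 4.2.1 and 13.5.1 categorise one seizure-freedom endpoint by severity at Baseline, so the protocol does treat severity as a Baseline attribute. What it lacks is any Baseline spans with which to compute it.
- *That the literal rule would flatter the drug.* The direction that gains responders is rare; the dominant effect lowers the rate.

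**Conclusion.** The conflict is real and affects the main secondary efficacy variable. SAP 8.1.1 and the four protocol places, followed literally, give a different class from SAP 8.1.2 and 8.1.5 for some infants, and 8.2.1 does not choose between them. The opposite classifications in the worked infants follow from the documents' own thresholds, whatever the distribution of seizures.

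The size of the effect on the reported rate does not follow from the documents. It ranged from under 1 to about 23 points across the assumed scenarios, almost all of it responders lost among infants severe at Baseline, and it depends on seizure length and on how many reductions fall between 50% and 80%. No single figure in that range should be quoted as the expected effect. The correction should be made before database lock, because it changes who counts as a responder in the comparison with historical rates.

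**What to change.** In SAP 8.1.1 and protocol Sections 1, 4.2.1, 10.1 and 13.5.1, delete the sentence that defines spans of a 2-hour period. Replace it with text to this effect: severity is classified on the Baseline Period only, using whichever of the 30-minute spans in SAP 8.1.2.1 and 8.1.2.2 were actually recorded; post-dose EEG does not affect the class; and SAP 8.1.5 governs the choice of target. Have SAP 8.2.1 cite 8.1.5 instead of Section 8.1 as a whole.

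Cover the short Baseline explicitly. In status epilepticus Baseline may last up to 30 minutes, so the second span may not exist and the first may be incomplete. State that the single recorded span is used and that more than 50% of recorded time in seizure counts as severe. Without this, a 15-minute recording that is all seizure would be non-severe under the 15-minute count in 8.1.2.1, although seizures fill 100% of it.

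The cost is SAP wording and a clarification in the next protocol amendment. No new data are needed.
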